## 13.7 Handling Missing Effectiveness and Safety Data

Missing data will be reported as a protocol deviation. The data will be interpreted and noted as incomplete. The Sponsor has the discretion to disqualify a patient due to a protocol deviation.

For incomplete assessments or missing data, analysis will utilize the last observation carried forward method.

All data analyses will be conducted on data from subjects with the necessary observed endpoint data (complete case analysis).

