## 9.7 Termination

Subjects may be terminated from the study at the discretion of the PI for reasons related to the study treatment that would jeopardize a subject's health and/or welfare if they were to continue in the study. Terminated subjects may be replaced. Terminated subjects may not be included in final data analysis. Notification of a subject termination should be made immediately to the Sponsor.

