# 9.8 Withdrawal

Subjects may be withdrawn from the study for non-treatment-related reasons only when no other option is possible. Reasons for withdrawal include, but are not necessarily limited to, voluntary withdrawal from the study by the subject.

The reason for withdrawal will be recorded on the appropriate Case Report Form. Withdrawn subjects may be replaced in the study. Notification of a subject withdrawal should be made immediately to the Sponsor.

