# **13.2** Analysis Populations and Handling of Dropouts

The Safety Population is defined as all patients who receive the Sonendo GentleWave System procedure.

The Efficacy Evaluable population is defined as all subjects who enroll in the study and who receive 100% of the Sonendo GentleWave Treatment (Treatment Complete Cohort) over the course of no more than two visits. Analysis of efficacy data will be performed using the Efficacy Evaluable population. Efficacy analyses will be based on observed data only; no imputation methods will be used. Dropout subjects will not be replaced.

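### Sections 13.2 and 13.7 give incompatible missing-data rules for the 24-month primary result, sections 13.2 and 9.7–9.10 conflict on replacement, and sections 9.7 and 13.7 allow exclusions that 13.2 does not list

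*Combined protocol and SAP*

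**What the plan says.** **Missing data.** Section 13.2: "Efficacy analyses will be based on observed data only; no imputation methods will be used. Dropout subjects will not be replaced". Section 13.7, whose heading covers both effectiveness and safety: "For incomplete assessments or missing data, analysis will utilize the last observation carried forward method". The sentence after that reads: "All data analyses will be conducted on data from subjects with the necessary observed endpoint data (complete case analysis"). Section 13.4 promises the 24-month proportion with an exact 95% interval and gives no rule for a missing 24-month result.

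**Replacement.** The second sentence of the 13.2 quote excludes it. Section 9.8 says: "Withdrawn subjects may be replaced in the study". Sections 9.7, 9.9 and 9.10 say the same of terminated, discontinued and lost-to-follow-up subjects.

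**Who is analysed.** Section 13.2 defines the Efficacy Evaluable population as "all subjects who enroll in the study and who receive 100% of the Sonendo GentleWave Treatment (Treatment Complete Cohort"), in no more than two visits. Section 9.7 concerns termination for treatment-related reasons "that would jeopardize a subject's health and/or welfare if they were to continue in the study", and adds: "Terminated subjects may be replaced. Terminated subjects may not be included in final data analysis". Section 13.7 adds: "The Sponsor has the discretion to disqualify a patient due to a protocol deviation".

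Section 13.0 defers analysis details to a statistical analysis plan. Nothing in the text available for review settles these three points.

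**The concern.** Carrying a value forward is imputation, so the carry-forward sentence contradicts both 13.2 and the sentence that follows it. Nothing limits it to safety, secondary or sensitivity analyses. Two analysts who each follow the text could report different denominators and different success counts.

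Missing 24-month outcomes are foreseeable. The primary endpoint in 3.1 needs radiographic as well as clinical findings. Section 7.19 allows telephone or mail follow-up that yields no radiograph, and 10.9.3 waives study radiographs for subjects who become pregnant.

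The exclusion wording matters because there is no concurrent control. Every subject receives the device and the comparator is a fixed 70%, so discretion over who is counted acts directly on the result. In 9.7, the words on inclusion in the final analysis can be read as permission or as a ban. In 13.7, disqualification is not tied to any analysis set, and missing data are themselves classed there as a deviation. If these choices were made after outcomes were seen, the analysis would no longer be prespecified.

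**Working it through.** **Inputs.** From 13.1: null rate 70%, planned rate 85%, two-sided 5% binomial test, 86 evaluable from 108 enrolled, and a 20% loss that combines loss to follow-up with Treatment Incomplete. From 13.4: exact 95% interval. Assumed: success means an exact lower limit above 70% (inferred from the sizing test, since 13.4 states no criterion); 86 observed 24-month outcomes; m further Treatment Complete subjects without a 24-month outcome but with an earlier value. I use m = 5 and m = 11. These are illustrative, because 13.1 does not split its 108 − 86 = 22 losses; 11 is half of them.

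**Step 1: the plan's own figure.** For n = 86 and p = 0.70, the smallest r with P(X ≥ r) ≤ 0.025 is 69 (tail 0.0223). Power at 85% is P(X ≥ 69) = 0.914, in line with the stated 90%. 86/0.8 = 107.5, rounded up to 108. The sample size reproduces.

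**Step 2: thresholds.** The exact (Clopper-Pearson) lower limit for x of n is the 2.5% quantile of Beta(x, n − x + 1).

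| Rule | n | Smallest x that clears 70% | Lower limit | One fewer |
|---|---|---|---|---|
| Complete case | 86 | 69 | 70.2% | 69.0% |
| Carry forward, m = 5 | 91 | 73 | 70.6% | 69.3% |
| Carry forward, m = 11 | 97 | 78 | 71.1% | 69.97% |

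**Step 3: chance that the rule changes the conclusion.** Let X ~ Bin(86, p) be the observed successes and Y ~ Bin(m, q) the carried successes, independent, and let T be the carry-forward threshold. The conclusions differ if X ≤ 68 and X + Y ≥ T, or if X ≥ 69 and X + Y < T. Summing over X:

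| True rate p | m | q = 70% | q = 85% |
|---|---|---|---|
| 85% | 5 | 4.6% | 2.7% |
| 85% | 11 | 10.4% | 4.0% |
| 70% | 11 | 1.3% | 1.6% |

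**Step 4: where the disagreement sits.** With m = 11:
- 68/86 misses on complete case. It clears on carry forward if at least 78 − 68 = 10 of 11 carried values are successes: chance 11% at q = 70%, 49% at q = 85%.
- 69/86 clears on complete case. It fails on carry forward if 8 or fewer of 11 are successes: chance 69% or 22%.
- 73/86 (about the planned rate, lower limit 75.5%) fails only if 4 or fewer of 11 are successes: 2.2% or 0.03%.

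The change can go either way and is concentrated near 69/86.

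**Step 5: the proposed sensitivity analysis.** If missing counts as failure, all T successes must come from the 86 observed. With m = 11 that is 78/86 = 90.7%, and P(X ≥ 78) at a true 85% is 8.6%. With m = 5 it is 73/86 = 84.9%, and P(X ≥ 73) is 58.5%.

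**The case against.** The text leans one way. Section 13.2 is the only statement specific to efficacy, the last sentence of 13.7 agrees with it, and the 13.1 arithmetic fits an analysis without imputation or replacement. The carry-forward sentence may be a leftover, or may have been meant for safety data or incomplete questionnaires, and a separate analysis plan could say so. That stands as a reason to expect an easy repair. It does not remove the conflict, because the sentence as written has no such limit.

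On exclusions, a terminated subject with no 24-month visit leaves a complete-case analysis anyway, so 9.7 may add little. That also stands. What remains is a subject who has a 24-month outcome and is removed by discretion. Replacement wording is an enrolment permission and does not by itself change who is analysed; no numerical effect is claimed for it.

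A reader might infer more than the documents support:
- That the rule flips the result with chance 11–69%. Those figures hold only if the observed count is exactly 68 or 69 of 86.
- That the sponsor's discretion inflates false success. Removing four subjects who are all failures at a true 70% rate would raise the chance of clearing the benchmark from 2.2% to 10.4%, but nothing in the plan supports that count or that selection. If only one of the four is a failure, the chance stays at 2.2%.
- That terminated subjects should count as failures in the primary analysis. Without a 24-month visit nothing was observed, so that would itself be imputation, which 13.2 bars.
- That the silence on retreated or extracted teeth belongs here. It is a gap in the endpoint definition rather than a contradiction, and a separate point.

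**Conclusion.** The three inconsistencies are on the page and should be fixed before outcomes are analysed. Under the stated success rule, with 86 observed outcomes and 5 to 11 more missing, the choice between carry forward and complete case changes the conclusion with probability about 3–10% at a true rate of 85% (carried values succeeding at 70–85%), and about 1% at a true rate of 70% with 11 missing and carried values also at 70%. These figures rest on an inferred criterion, assumed missing counts, and carried values independent of the observed count. Bias from discretionary exclusion is possible, not shown. The stated sample size is not in error.

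**What to change.** 1. Delete the carry-forward sentence in 13.7 and keep the observed-data rule of 13.2 as the single primary method. The exact interval in 13.4 can stay.
2. State that no Treatment Complete subject with an observed 24-month outcome can be removed from the primary analysis, either by termination under 9.7 or by sponsor disqualification under 13.7.
3. Reconcile 9.7 to 9.10 with 13.2 on replacement. Any replaced Treatment Complete subject who has an observed outcome stays in the analysis.
4. Add one sensitivity analysis on all Treatment Complete subjects that counts missing 24-month outcomes as failures. Label it a conservative bound and not a success criterion: step 5 shows that it would often miss 70% even at the planned rate.

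The cost is wording in the protocol and analysis plan and one extra table. No subjects, visits or assessments are added.

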## **13.8 Handling Post-Market Analysis**

With the addition of Post Market enrollment subjects the sponsor may elect to provide separate subset analysis of pre and post market enrollment.

## 14.0 DATA REPORTING

A CRF casebook will be used for each subject enrolled in the study. All clinical data generated in the study will be reviewed for quality assurance review, data entry, and statistical analysis. All forms will be reviewed for completeness; evident recording errors will be rectified by contact with the appropriate clinical site.

The appropriate CRF will be completed by the PI or a clinical site designee after each visit. The PI will sign the CRFs to indicate verification and approval. All CRFs will be completed in a legible

manner in blue or black ink. Any corrections will be made by drawing a single line through the incorrect entry, entering the correct information, and initialing and dating the change.

If there is a discrepancy between a CRF and the source document and any significant data within the CRF is changed, the PI should re-sign the form to indicate verification and approval of the change(s).

If no Second Day Procedure, Protocol Deviation, AE, or AE Resolution occurred, then the associated CRF does not need to be completed or collected.

CRFs should be completed within two (2) weeks of a subject's study visit. The original signed forms, not copies, will be returned to the Sponsor.

All redacted source documentation with PI signature should be provided to the Sponsor for filing after each study visit. If changes are made to the source documents after PI signature, the updated source documents should be provided to the Sponsor for filing.

Both Screening Dentists and PIs conduct a medical and dental review and assessments on a patient. The Screening Dentist performs this review only as part the pre-screening process. Information collected by a Screening Dentist will not be included as study data (i.e. Screening Form, pre-screening radiographs, and dental notes). Only information collected by a PI will be used as study data. The data collected or assessments performed by a PI supersede those completed by a Screening Dentist. Source data verification will occur using the subject's dental file.

# 15.0 STUDY MONITORING

In accordance with applicable regulations and Good Clinical Practice (GCP), the PI and/or Sponsor will check and assess the progress of the study, review the data collected, conduct source document verification, and identify any issues and address resolutions. These activities are conducted to verify that the data are authentic, accurate, complete, that the safety and rights of subjects are being protected, and that the study is conducted in accordance with the currently approved protocol (with amendments), and all applicable regulatory requirements.

If a clinical monitor becomes aware that a PI is not complying with the requirements mentioned above, the monitor will notify the Sponsor. The Sponsor will evaluate the noncompliance.

Monitoring visits will be performed at regular intervals and according to the study monitoring plan to ensure appropriate study conduct and integrity of the data being recorded. Any discrepancies in the data will be noted and data clarifications or queries will be issued by the monitor to correct these discrepancies or obtain additional information. Following completion of a monitoring visit, monitoring reports will be generated and will be sent to the Sponsor for review and approval.

The PI agrees to allow the monitor direct access to all relevant documents and agrees to allocate his/her time and the time of his/her staff to the monitor to discuss findings and any relevant issues.

Information collected by a Screening Dentist is considered part of the pre-screening process and none of this information will be monitored or utilized as study data (i.e. Screening Form, pre-screening radiographs, dental notes, and correspondence).

The monitoring will be performed by a Sonendo representative, who will also assess the progress of the study and identify any concerns that result from device performance, review of the PI's study records, study management documents, and subject informed consent documents. This review includes adherence to the study protocol, IRB review of the study and its progress, and maintenance of records and reports.

# 16.0 ETHICAL AND REGULATORY CONSIDERATIONS

This protocol was designed and will be conducted, recorded, and reported in compliance with the principles of Good Clinical Practice (GCP) regulations. These requirements are stated in global regulations as well as "Guidance for Good Clinical Practice," International Conference on Harmonization (ICH), and the most recent guidelines of the Declaration of Helsinki of Technical Requirements for Registration of Pharmaceuticals for Human Use.

# **17.0 SPONSOR RESPONSIBILITIES**

The Sponsor agrees to comply with the FDA 21 CFR Part 812 for all applicable regulations for nonsignificant risk devices.

# **18.0** INVESTIGATOR'S RESPONSIBILITIES

It is understood that the term "Investigator" as used in this protocol and on Case Report Forms refers to the Principal Investigator or a member of the staff that the Principal Investigator has trained and designates to perform a certain duty. The Principal Investigator is ultimately responsible for the conduct of all aspects of the study.

The PI must have prior knowledge and training on GCP and Human Subjects Protection.

The PI must receive training for the Sonendo GentleWave System prior to commencement of the study.

The PI must have written approval from the Institutional Review Board prior to enrolling a patient into the study. The Sponsor must be informed about the approval by receipt of written confirmation.

The PI will ensure that this study is conducted in full accordance with the Declaration of Helsinki. It is the responsibility of the PI to obtain written informed consent from each individual participating in the study, after adequate explanation of the aims, methods, objectives, and potential hazards of the study. The PI or designee must also explain to subjects that they are completely free to refuse to enter the study or to withdraw from it at any time.

The PI should ensure the accuracy, completeness, legibility and timely reporting of the study required data.

The PI is required to sign an Investigator's Agreement or Investigator's Contract. This document includes information on the Investigator's obligations with respect to the use of the device, informed consent, and reporting of AEs. By signing the Investigator's Agreement, the PI acknowledges assurance to the Sponsor and compliance with the protocol and study obligations.

No changes to this protocol can be made without the Sponsor's written approval.

## **18.1** Retention of Records

The PI is responsible for maintaining the following study records and for providing access to these records by the Sponsor, IRB, and FDA for audit and inspection:

- Source documents (e.g., medical and dental records) including subject's case history, documentation that informed consent was obtained prior to study participation, and a description of circumstances if no informed consent was obtained
- Case Report Forms
- Signed and dated Informed Consent Forms
- Patient's Audio-Video Recording and Photograph Release Form
- Electronically saved audio-video recordings and photographs of individual study cases
- Correspondence with the Sponsor, Medical Monitor, IRB, FDA and other Investigators including required reports
- Study protocol and any amendments
- Continuing review reports to IRB and Sponsor annually or as required by IRB
- Any other records required by the IRB

The PI is required to maintain the records for at least two (2) years following the latter of either the date when the study is terminated or completed, or the date that the records are no longer required for purposes of supporting a marketing application.

## **18.2** Study Documents

This protocol, the subject Informed Consent Form (ICF) and amendments to the ICF, if applicable, must be reviewed and approved by an IRB that is operating in accordance with local procedures and the abbreviated requirements for 21 CFR Parts 812, before enrollment of subjects. In developing a site-specific Informed Consent Form, the PI must comply with the guidelines for the

content of Informed Consent Forms. Any site-specific Informed Consent Form and ICF amendments must be reviewed and approved by the Sponsor prior to submission to the IRB.

It is the responsibility of the PI to obtain and maintain approval for the Study Protocol, ICF and ICF amendments and to keep the IRB informed of serious adverse events and any amendments to the protocol. It is also the PI's responsibility to maintain a file of all correspondence with the IRB and to forward copies of that correspondence to the Sponsor, or the Sponsor's representative.

## **18.3** Subject Selection

The PI is responsible for ensuring that all subjects entering the study conform to the subject Inclusion and Exclusion Criteria and are willing and able to complete the required study visits.

## **18.4** Subject Informed Consent

Before any study related procedures are completed or a patient is enrolled into the study, each potential subject will be given appropriate explanation of the study. Once the essential information has been provided and the Investigator is assured that the candidate understands the implications of participating in the study, the subject will be asked to give his/her consent to participate in the study by signing the Informed Consent Form. The person performing the consent process and the Investigator must sign the ICF. The subject will be given a copy of the executed ICF.

# 18.5 Confidentiality

The PI will ensure that patient names and data will be kept confidential. The Investigator and study staff agree to comply with the HIPAA Privacy Rule. In case of adverse and serious adverse event reporting, only the subject initials and subject ID shall be employed and the patient's identity will not be disclosed.

Subject identity will only be revealed in the case that patient confidentiality would compromise patient or study safety.

# **19.0 INVESTIGATOR TRAINING**

All PIs must participate in a training program conducted by the Sponsor or designated representative.

There will be up to five (5) Roll-In cases per PI. The number of cases is dependent on the training and Sonendo experience level of the PI. The Sponsor may elect to disregard one (1) to five (5) of the Roll-In cases for a particular PI. PIs who will be performing root canal therapy (RCT) with the Sonendo GentleWave System must receive a Certification of Training from Sonendo prior to their first Non-Roll-In subject enrollment.

Requirements for certification of an Investigator include:

- 1. Completion of didactic instruction on the function, theory and application of the Sonendo GentleWave System.
- 2. Training on the protocols for access, treatment, and obturation, review of patient eligibility, Inclusion and Exclusion Criteria, and the rationale for the criteria, as well as details on all study methods.
- 3. Completion of a comprehensive laboratory training on the procedure employed for Sonendo GentleWave treatment. Practice cases with ex-vivo extracted teeth will be performed onsite in the Sonendo, Inc. laboratory and tooth treatment facility.
- 4. Completion of up to five (5) successful Roll-In cases in an in-vivo environment.

## 19.1 Roll-In Subjects

There will be up to five (5) Roll-In cases per PI. The number of the Roll-In subjects will be determined by Sonendo during training and will depend on the PI's level of experience with the Sonendo GentleWave System. The Sponsor may elect to disregard one (1) to five (5) of the Roll-In cases for a particular PI.

Roll-in subjects will be provided Subject IDs different from that of Non Roll-In subjects. The second three (3) digit code begins with an R to designate the subject as a Roll-In. The R is followed by a sequential two digit number for that site. Therefore, the first Roll-In subject enrolled at site 101 is 101-R01, the second is 101-R02, and so forth. The data obtained from Roll-In cases will be collected, but may not be included in the final data analysis.

